## **5.3 Dose Limiting Toxicities**

A dose limiting toxicity (DLT) is defined as any toxicity that occurs that is considered at least “possibly related to the study drug administration”. Only DLT’s that occur prior to initiation of cycle 2 will be used to determine dose escalation/de-escalation decisions.

DLT criteria are defined as follows:

1. Any non-hematologic toxicity greater and/or equal to grade 3, except for:
  - Alopecia
  - Untreated nausea or vomiting;
  - Untreated constipation or diarrhea;
  - Untreated dehydration or fatigue uncontrolled;
  - Any liver function test including AST/ALT, GGT, Alkaline phosphatase elevation that has returned to grade 1 or baseline by day1 of cycle 2;
2. Grade 4 neutropenia lasting more than 5 days despite GCS-F support;
3. Febrile neutropenia (ANC <  $1000/\text{mm}^3$  with a single temperature of  $> 38.3^\circ\text{C}$  or sustained temperature of  $\geq 38^\circ\text{C}$  for over one hour);
4. Any grade 4 thrombocytopenia or grade 3 thrombocytopenia with clinically significant bleeding or any grade-3 thrombocytopenia requiring platelet transfusion
5. Grade 4 anemia unexplained by underlying disease involvement;

6. Failure to meet the required blood parameters for cycle 2 day 1.

Management and dose modifications associated with adverse events will be described in the following sections 7.0, 7.1, 7.2 (Dose selection, dose delays, dose modification).

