#### **Attribution of Toxicity:**

When study interventions are administered in combination, attribution of an adverse event to a single component is likely to be difficult. Therefore, while the investigator may attribute a toxicity event to the assigned treatment combination, to pralatrexate alone (Arm A or B), to decitabine alone (Arm B or C) or to pembrolizumab alone, for adverse events listed in Table 10, both (all, for Arm B) interventions must be held according to the criteria in Table 10 Dose Modification and Toxicity Management Guidelines for Immune-Related Adverse Events.

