### 7.3.2 Pralatrexate

Patient treated with pralatrexate are at risk of developing mucositis. The risk of developing mucositis can be lowered by pretreating patient with leucovorin 15 mg PO BID that has to be held the day before, day of and day after pralatrexate administration. The treatment with leucovorin will be given with treatment as noted above but can be given at the treating physician's discretion for pralatrexate related mucositis (i.e. in schedule delays). Pralatrexate and decitabine can induce hematologic toxicity that should be address with Neupogen/Neulasta support at the treating physician's discretion and as suggested in Table 12 and Table 13.

Doses may be omitted or reduced based on patient tolerance. Omitted doses will not be made up for at the end of the cycle; once a dose reduction occurs for toxicity, there will be no re-escalation. For dose modifications and omissions, use the suggested guidelines in Table 11, Table 12 and Table 13 below.

Table 11: Suggested Guidelines for Pralatrexate Dose Modifications for Mucositis after Cycle 1

Mucositis Grade a on the Day of Treatment	Action	Dose upon recovery to Grade ≤ 1
Grade 2	Omit dose	Maintain dose level
Grade 2 recurrence	Omit dose	Reduce to one dose level below
Grade 3	Omit dose	Reduce to one dose level below
Grade 4	Stop therapy	No further treatment with pralatrexate

a Per NCI CTCAE, Version 3.0

Table 12: Suggested Guidelines for Pralatrexate Dose Modifications for Hematologic Toxicities

Blood Counts on the Day of Treatment	Duration of Toxicity	Action	Dose upon re-start
Platelets < 50,000/µL	1 week	Omit dose	Continue prior dose
	2 weeks	Omit dose	Reduce to one dose level below
	>2 weeks	Stop therapy	No further pralatrexate
ANC 500-1,000/µL and no fever	1 week	Omit dose	Continue prior dose
ANC 500-1,000/µL with fever (a single temperature of > 38.3°C or sustained temperature of ≥ 38°C for over one hour) or ANC <500/µL	1 week	Omit dose, give G-CSF or GM-CSF	Continue prior dose with G-CSF or GM-CSF support
	2 weeks or recurrence	Omit dose, give G-CSF or GM-CSF	Reduce to one dose level below with G-CSF or GM-CSF support
	>2 weeks or 2nd recurrence	Stop therapy	No further pralatrexate

Table 13: Suggested Guidelines for Pralatrexate Dose Modifications for All Other Treatment Related Toxicities

Toxicity Grade a on the Day of Treatment	Action	Dose upon recovery to Grade ≤ 2
Grade 3	Omit dose	Reduce to one dose level below

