- **Hepatotoxicity:** Liver function test abnormalities have been observed with pralatrexate use. Persistent abnormalities may indicate hepatotoxicity and may require dosage modification as indicated in table 13 and in the FDA package insert.

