    - Treat with an initial dose of IV corticosteroid followed by oral corticosteroids. Withhold or permanently discontinue treatment, at discretion of the investigator or treating physician. When symptoms improve to Grade 1 or less, steroid taper should be started and continued over no less than 4 weeks.
- **Hepatic:**
  - For **Grade 2** events, monitor liver function tests more frequently until returned to baseline values (consider weekly).
    - Treat with IV or oral corticosteroids
  - For **Grade 3-4** events, treat with intravenous corticosteroids for 24 to 48 hours. Permanently discontinue treatment for grade 4 or grade 3 toxicity.
  - When symptoms improve to Grade 1 or less, a steroid taper should be started and continued over no less than 4 weeks.
- **Renal Failure or Nephritis:**
  - For **Grade 2** events, withhold treatment and treat with corticosteroids.
  - For **Grade 3-4** events, treat with systemic corticosteroids. Permanently discontinue treatment.
  - When symptoms improve to Grade 1 or less, steroid taper should be started and continued over no less than 4 weeks
- For other immune related adverse events (IRAE) including myocarditis, encephalitis and Gullian-Barre and further clarification of the above mention IRAE refer to table 10 and section 7.3.1**Management of Infusion Reactions:** Signs and symptoms usually develop during or shortly after drug infusion and generally resolve completely within 24 hours of completion of infusion.

Treatment guidelines for subjects who experience an infusion reaction associated with administration of pembrolizumab are in Table 14 below.

Table 14: Infusion Reaction Treatment Guidelines

NCI CTCAE Grade	Treatment	Premedication at subsequent dosing
Grade 1 Mild reaction; infusion interruption not indicated; intervention not indicated	Increase monitoring of vital signs as medically indicated until the subject is deemed medically stable in the opinion of the investigator.	None
Grade 2 Requires infusion	Stop Infusion and monitor symptoms.	Subject may be premedicated 1.5h ( $\pm$ 30 minutes) prior to infusion of

NCI CTCAE Grade	Treatment	Premedication at subsequent dosing

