## **7.10 Subject Withdrawal/Discontinuation Criteria**

Subjects may withdraw consent at any time for any reason or be dropped from the trial at the discretion of the investigator should any untoward effect occur. In addition, a subject may be withdrawn by the investigator or the Sponsor if enrollment into the trial is inappropriate, the trial plan is violated, or for administrative and/or other safety reasons. Specific details regarding discontinuation or withdrawal are provided in Section 9.1.8– Other Procedures.

A subject must be discontinued from the trial for any of the following reasons:

- The subject or legal representative (such as a parent or legal guardian) withdraws consent.
- Confirmed radiographic disease progression
  - Note:* For unconfirmed radiographic disease progression, please see LYRIC criteria
  - Note:* A subject may be granted an exception to continue on treatment with confirmed radiographic progression if clinically stable or clinically improved, please see Section 7.11
- Unacceptable adverse experiences as described in Section 7.3
  - a. Note: if any drug in the combination for the assigned arm is discontinued and/or is required to be held for an adverse event per section 7.0 for >2 weeks, all study treatment should be discontinued.
- Treatment needs to be held (based on section 7.0) for an adverse event delaying treatment for > 2 weeks
- Intercurrent illness that prevents further administration of treatment
- Investigator's decision to withdraw the subject
- The subject has a confirmed positive serum pregnancy test
- Noncompliance with trial treatment or procedure requirements
- The subject is lost to follow-up
- Completed 24 months of uninterrupted treatment with pembrolizumab or 35 administrations of pembrolizumab, whichever is later.
- Administrative reasons

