$$L_m(\theta_m) = \prod_{i \in \{1, 2, 3, 5, 8\}} \left( p_{mi}^{\exp(\theta_m)} \right)^{y_i} \left( 1 - p_{mi}^{\exp(\theta_m)} \right)^{n_i - y_i},$$

$y_i$  = the number of DLTs, and  $n_i$  = the number of treated patients in combination  $i$ . The ordering  $h$  with the largest likelihood is chosen and, within this ordering, DLT probability estimates are updated for each combination. If there is a tie between the likelihood values of two or more orderings, then the selected ordering  $h$  is randomly chosen from among the tied orderings. After accrual of each patient cohort into the trial, the DLT probability estimates,  $\tilde{R}(d_i)$ , are updated via

$$\tilde{R}(d_i) = p_{hi}^{\exp(\tilde{\theta}_h)}; \quad \tilde{\theta}_h = \arg \max L_h(\theta_h).$$

The DLT probability estimates are used to sequentially allocate participants according to the following rules:

1. If the most recent participant accrued to the study **does not** experience a DLT, then the recommended combination for the next participant will be the combination indicated by the model to have an estimated DLT rate closest to 25%. Escalation of both agents simultaneously or escalation of more than one dose level of either agent is not allowed.
2. If the most recent participant accrued to the study **does** experience a DLT:
  - a. If the DLT is mucositis or thrombocytopenia or mucositis plus neutropenia and/or thrombocytopenia, then the recommended combination for the next participant will be restricted to either the current combination administered to the most recent participant or to de-escalation of one dose level of Pralatrexate, based on which combination has an estimated DLT rate closest to 25%.
  - b. If the DLT is neutropenia or neutropenia and thrombocytopenia, then the recommended combination for the next participant will be restricted to either the current combination administered to the most recent participant or to de-escalation of one dose level of Decitabine, based on which combination has an estimated DLT rate closest to 25%

The study will sequentially repeat the estimation procedure after the enrollment and follow-up of each cohort. The allocation procedure will be repeated until sufficient information about the MTD has been obtained according to the stopping rules described below.

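### A recovered immune-related grade 3-4 AST/ALT elevation ends all study treatment but, read naturally, counts as a non-DLT in the dose-finding likelihood

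*Protocol*

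**What the plan says.** **What counts as a DLT (section 5.3).** The general rule is "Any non-hematologic toxicity greater and/or equal to grade 3, except for" a short list, which includes "Any liver function test including AST/ALT, GGT, Alkaline phosphatase elevation that has returned to grade 1 or baseline by day1 of cycle 2". That item sets no upper grade and does not exclude immune-related or steroid-treated events. Item 6 makes failure to meet the cycle 2 day 1 blood parameters a DLT. Section 5.4 sets the AST/ALT limit at 2.0 x ULN, or 3.0 x ULN or baseline with liver involvement. No item refers to permanent discontinuation.

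**What happens to the participant.** For immune-related AST/ALT elevation of grade 3 or 4 (above 5.0 x ULN if baseline is normal), Table 10 requires permanent discontinuation of pembrolizumab. The hepatic paragraph of section 7.8.2 says the same: "Permanently discontinue treatment for grade 4 or grade 3 toxicity". The attribution paragraph of section 7.3.1 extends the action to the partner drugs: "for adverse events listed in Table 10, both (all, for Arm B) interventions must be held according to the criteria in Table 10". Section 7.10 ends all study treatment "if any drug in the combination for the assigned arm is discontinued and/or is required to be held for an adverse event" for more than two weeks.

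**How the DLT is used (section 10).** The DLT is binary, cohorts are of size 1, the target is 25%, and the model is refitted after each participant. An arm closes when the recommended level already has 7 participants. Section 10.4 replaces only enrolled subjects who receive no treatment.

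**Arm B allocation after a DLT (section 10.2).** Rule 2 has two branches. Branch 2a covers mucositis or thrombocytopenia, including mucositis combined with cytopenias. Branch 2b begins "If the DLT is neutropenia or neutropenia and thrombocytopenia, then the recommended combination for the next participant will be restricted to either".

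**The concern.** Exempting transient laboratory elevations is sensible when the participant goes on with treatment. Here the same protocol requires that treatment stop for good, and recovery does not reverse this. The management rules treat the event as intolerable; the DLT definition, on its natural reading, treats it as tolerated.

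The DLT indicator is the only toxicity input to allocation, to the 7-participant closing rule and to the MTD. A participant scored this way adds one to n and nothing to y at the assigned dose, which pulls the estimated DLT rate down. DSMC review would keep the event visible but would not alter the likelihood.

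A separate gap lies in Arm B. Grade 4 anemia and grade 3 pneumonitis are DLTs under section 5.3, but rule 2 does not say where the next participant goes after one. The same would hold for a liver event scored as a DLT.

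**Working it through.** **1. Can such a participant escape every DLT item?**

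- The grade 3-4 elevation meets the general rule but is exempt if it is back to grade 1 or baseline by cycle 2 day 1.
- Table 10 starts grade 2 above 3.0 x ULN (normal baseline), so grade 1 extends to 3.0 x ULN. Without liver involvement, section 5.4 requires 2.0 x ULN or less. Recovery only to between 2.0 and 3.0 x ULN therefore still fails item 6 and is a DLT.
- Recovery to 2.0 x ULN or less, or to the wider allowance with liver involvement, passes item 6. No other item applies.
- The restart paragraph of section 7.3.1 does not rescue the case. It allows a restart only in line with Table 10, which here says discontinue.

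**2. Reproducing the stated dose assignments.** The model is p_i^b with b = exp(a), fitted by maximum likelihood. The skeleton for Arms A and C is 0.08, 0.15, 0.25 for Levels -2, -1 and 1. When all data are at the top level, b = ln(y/n)/ln(0.25).

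- Arm A, 1/5: b = 1.161; estimates 0.053, 0.111, 0.200. Closest to 25% is Level 1, as section 10.1 states.
- Arm C, 2/4: b = 0.5; estimates 0.283, 0.387, 0.500. Closest is Level -2; the no-skipping rule limits the move to Level -1, as stated.
- Arm B, 1/4 at Combination 8: b = 1; estimate 0.250. It stays at Combination 8, as stated.

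**3. Scoring one such event as a DLT, by position.**

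| Position | Scored non-DLT | Scored DLT | Next step |
|---|---|---|---|
| Arm A, participant 6 | 1/6: 0.167 at Level 1 | 2/6: 0.333 at Level 1, 0.222 at Level -1 | stay, versus move to Level -1 |
| Arm A, participant 7 (no DLT in 6) | 1/7: 0.143 at Level 1 | 2/7: 0.286 at Level 1, 0.180 at Level -1 | both close the arm at Level 1 |
| Arm C, participant 5 (at Level -1) | coherence rule forbids a move down | 0.528 at Level -1, 0.428 at Level -2 | stay, versus move to Level -2 |

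For example, at 2/6, b = ln(1/3)/ln(0.25) = 0.792 and 0.15^0.792 = 0.222. The distances from 0.25 are 0.083 at Level 1 and 0.028 at Level -1. At 2/7, b = 0.904 and 0.15^0.904 = 0.180. The distances are 0.036 and 0.070, so Level 1 is kept.

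**4. Arm B, only if an allocation branch existed for a liver DLT.** With data only at Combination 8 the five orderings tie, and the estimate there equals y/n.

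- Participant 5: 0.200 (stay) versus 0.400 (move down).
- Participant 6 (no DLT in 5): 0.167 (stay) versus 0.333. The combination with skeleton value 0.174, which is 5 or 6 depending on the ordering, becomes 0.174^0.792 = 0.250 (move down).
- Participant 7 (no DLT in 5 or 6): 0.143 versus 0.286, with the next best at 0.174^0.904 = 0.206. There is no change.

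**The case against.** **DLT scoring and patient management serve different ends.** Nothing in the protocol says that a treatment-ending toxicity must be a DLT, so this is not a contradiction in the strict sense. That stands. It leaves a design choice that is hard to defend, because the exemption suits elevations after which treatment continues.

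**The non-DLT score is an inference.** Section 10.2 asks for at least one cycle of follow-up, and the exemption is judged at a cycle 2 day 1 that this participant never starts. The text does not say whether the participant is exempt, non-evaluable or a DLT. This also stands. Non-DLT is the natural reading, since section 10.4 replaces only untreated subjects, but the uncertainty is itself a reason to clarify.

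**Pembrolizumab is fixed at 200 mg.** A reader might infer that a dose-dependent toxicity is being hidden. For the immune-related event the documents do not support that, and scoring it may lower a partner drug that did not cause it. Against this, section 7.3.1 says that attribution to a single component is likely to be difficult, and section 10.1 defines the MTD as a dose combination.

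**The scope is narrow.** A reader might take section 7.3.1 to mean that Table 10 applies to any liver event, whichever drug is blamed. It does not: Table 10 covers immune-related events, and section 7.8.2 applies when the event is judged related to pembrolizumab. A reader might also extend the point to pralatrexate, because "Liver function test abnormalities have been observed with pralatrexate use" and section 7.8.1 refers to Table 13. That table is headed "Suggested Guidelines for Pralatrexate Dose Modifications for All Other Treatment Related Toxicities", section 7.3 opens with toxicity beyond cycle 1, and grade 3 there means a reduction, not a stop. The point does not rely on it.

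**The event is uncommon.** It must be immune-related, grade 3-4, arise in cycle 1 and resolve before cycle 2. In Arms B and C pembrolizumab starts on day 8, leaving about three weeks for both. This is fair.

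**Conclusion.** The point holds as a minor defect of definition. A participant whose immune-related grade 3-4 AST/ALT elevation recovers to within the section 5.4 limits is removed for toxicity and, on the natural reading, counted as having tolerated the dose.

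Its size depends on position. One event changes the next dose for Arm A participant 6 and Arm C participant 5, but not for Arm A participant 7 after no DLT in participant 6. The Arm B effects require an allocation branch that does not yet exist. The Arm A and C results assume the data stated in section 10.1 and the no-skipping and coherence rules of section 10.2.

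A reader might infer that the MTD will be materially biased. The documents do not support that: they give no rate for the event, and the average effect on MTD selection is probably small. Any probability of seeing one would rest on an assumed rate and on pooling three arms with separate likelihoods.

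The missing Arm B branch is a separate defect. It holds whatever view is taken of liver tests and adds no weight to the main point.

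**What to change.** **Main point.** State in section 5.3 and on the DLT CRF that a toxicity before cycle 2 is a DLT if it is at least possibly related and the protocol requires permanent discontinuation of a study drug for it, and that the liver-test exemption does not apply to such events. The exemption stays for elevations after which treatment continues. The sentence also settles the scoring of a participant who never reaches cycle 2.

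Recheck the participants already in the likelihood against the new wording: 5 in Arm A, 4 in Arm C and 4 in Arm B, 13 in all.

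**Separate point.** Add a branch 2c to the Arm B rules in section 10.2 for every DLT not covered by 2a or 2b: stay, or de-escalate one level of either agent, whichever has an estimated DLT rate closest to 25%.

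**Cost.** One sentence, one CRF item, a review of 13 records and one allocation branch. The downside is that slightly more DLTs may be counted, so the pralatrexate or decitabine dose may be lowered for an event due to fixed-dose pembrolizumab. The sponsor should accept that openly in the text.

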#### **5.4 Required Blood Parameters and Other Investigations Prior to Each Treatment**

Before the start of each cycle, patients should be reassessed, and the following criteria must be fulfilled:

- Absolute neutrophil count (ANC)  $> 1000/\mu\text{L}$
- Platelet count  $\geq 50,000/\mu\text{L}$
- Serum creatinine concentration  $\leq 2.0 \times$  institutional ULN or  $\leq$  baseline, or creatinine clearance  $> 50 \text{ ml/min}$  or baseline
- AST and ALT  $\leq 2.0 \times$  ULN or  $\leq 3.0 \times$  institutional ULN or baseline in presence of demonstrable lymphoma involvement of liver
- Bilirubin concentration  $\leq 1.5 \times$  ULN or direct bilirubin  $\leq$  ULN for patients with total bilirubin levels  $> 1.5 \times$  ULN
- Recovery of any drug-related non-hematological AE to grade  $\leq 1$ , unless otherwise indicated
- The above blood parameters are required to start day 1 treatment of every cycle with decitabine but do not need to be evaluated on day 2, day 3, day 4 and day 5 of each cycle unless clinically indicated.

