### **Safety of Decitabine**

Most common adverse reactions (>50%) are neutropenia, thrombocytopenia, anemia, and pyrexia. Following the first cycle of DACOGEN treatment, if any of the following non-hematologic toxicities are present, DACOGEN treatment should not be restarted until the toxicity is resolved: 1) serum creatinine  $\geq 2$  mg/dL; 2) SGPT, total bilirubin  $\geq 2$  times ULN; 3) and active or uncontrolled infection.

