### 7.2 Dose Delays

These dose delays apply to all drugs and patients on all study arms. Additional delays may apply for specific drugs (see sections 7.3.1 and 7.3.2 below).

- Study drugs can be administered within 48 hours of their scheduled time.
- Study drugs will be held for DLT and any grade 3/4 toxicity not addressed in [section 5.3](#) until the AE returns to grade  $\leq 2$  unless otherwise specified in the sections below.
- If the interruption lasts for more than 14 days, study treatment will be discontinued.

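### Section 5.4 admits to a decitabine cycle some participants whom Section 4.3.3 says should not restart, and Sections 5.4 and 7.2 give different recovery grades with none named as governing the start of a cycle

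*Protocol*

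**What the plan says.** Protocol Section 5.4 is a mandatory list: "Before the start of each cycle, patients should be reassessed, and the following criteria must be fulfilled". It is tied to decitabine by its last item: "The above blood parameters are required to start day 1 treatment of every cycle with decitabine". Its relevant limits are:

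- creatinine: at most 2.0 x institutional ULN, or no higher than baseline, or clearance above 50 mL/min or at baseline;
- AST and ALT: at most 2.0 x ULN, relaxed to 3.0 x ULN or baseline "in presence of demonstrable lymphoma involvement of liver";
- bilirubin: total at most 1.5 x ULN, or, when total is higher, direct bilirubin within ULN;
- drug-related non-hematological events: recovered to grade 1 or lower, subject to a general exception that names no other section.

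Section 4.3.3, under Safety of Decitabine, lists creatinine of 2 mg/dL or more, SGPT or total bilirubin of 2 x ULN or more, and active or uncontrolled infection. If any is present after the first cycle, "DACOGEN treatment should not be restarted until the toxicity is resolved".

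Section 7.2 covers all drugs and all arms. It holds study drugs for a DLT or grade 3/4 toxicity until the event is at grade 2 or lower, and adds: "If the interruption lasts for more than 14 days, study treatment will be discontinued". Table 13 (pralatrexate, all other treatment-related toxicities) also uses recovery to grade 2 or lower. Section 7.10 discontinues a subject whose treatment is held for more than 2 weeks for an adverse event.

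**The concern.** A site deciding on day 1 whether to give the next decitabine cycle finds two sets of laboratory limits that do not agree, one of which also has an infection condition. A site deciding whether a toxicity has recovered enough finds two grades. No section says which prevails for a cycle-start dose.

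The stake is first participant safety: under one section a participant is dosed, under another the same participant waits. It is also retention, because a hold that passes 14 days ends study treatment. The laboratory and infection conflict concerns Arms B and C, which contain decitabine. The recovery-grade conflict can arise in all three arms.

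**Working it through.** The protocol states no calculated figure here, so the check puts test cases through each rule.

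**Creatinine.** Section 4.3.3 bars restart at 2.0 mg/dL or more. Section 5.4 allows up to 2.0 x ULN. The institutional ULN is not given, so it is assumed over a range. The conflict band runs from 2.0 mg/dL to 2.0 x ULN:

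| Assumed ULN (mg/dL) | 5.4 limit = 2.0 x ULN (mg/dL) | Passes 5.4, barred by 4.3.3 |
|---|---|---|
| 0.9 | 1.8 | none |
| 1.0 | 2.0 | exactly 2.0 only |
| 1.1 | 2.2 | 2.0 to 2.2 |
| 1.2 | 2.4 | 2.0 to 2.4 |
| 1.3 | 2.6 | 2.0 to 2.6 |
| 1.4 | 2.8 | 2.0 to 2.8 |

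This is the ULN limb alone. The baseline and clearance alternatives in 5.4 can admit a value of 2 mg/dL or more at any ULN.

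**ALT (SGPT) and total bilirubin.**

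| Case | 5.4 | 4.3.3 |
|---|---|---|
| ALT 2.5 or 3.0 x ULN, liver involvement | start | do not restart |
| ALT exactly 2.0 x ULN, no liver involvement | start | do not restart |
| Total bilirubin 2.5 x ULN, direct within ULN | start | do not restart |
| Total bilirubin 1.8 x ULN, direct above ULN | hold | not barred |

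Table 6 admits participants with AST/ALT up to 5 x ULN when there are liver metastases. Someone entering at 4 x ULN could therefore keep passing 5.4 on the baseline alternative, while 4.3.3 would bar restart unless a pre-existing elevation is read as not being a toxicity. The last row shows that neither set is stricter throughout.

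**Infection.** Section 4.3.3 bars restart. Section 5.4 has no matching line, so an infection judged not drug-related does not stop a cycle under 5.4.

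**Recovery grade.** Take a drug-related, non-immune, non-hematological grade 3 event that has fallen to grade 2 on day 1 of the next cycle.

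- Section 7.2: the hold is lifted.
- Section 5.4: the cycle may not start.
- If the event stays at grade 2 and the delay passes 14 days, Sections 7.2 and 7.10 end treatment.

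The exception clauses do not settle this. Section 7.2 gives way only to sections that follow it, and 5.4 precedes it. The exception in 5.4 names no section. The general instruction in Table 10 resumes treatment at grade 1 or lower, in line with 5.4, so immune-related events are outside the example, as is mucositis under Table 11.

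**The case against.** **Section 4.3.3 is background.** It sits under Background & Rationale, uses the brand name, and reads like a label summary. Section 5.2 sends the reader to the package insert or investigator's brochure only for matters the protocol does not specifically mention. Creatinine, ALT and bilirubin are mentioned in 5.4, so there is a fair textual argument that 5.4 prevails on those. That argument stands in part. But the sentence in 4.3.3 is itself protocol text worded as an instruction, Section 7 has no decitabine table, and Section 7.3 allows modifications after cycle 1 to follow the insert. On infection 5.4 is silent, so the 5.2 rule does not displace 4.3.3; there the defect is an omitted condition rather than opposing limits.

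**Sections 5.4 and 7.2 can both be obeyed.** One may govern the start of a cycle and the other the release of a hold, including for doses given mid-cycle (pralatrexate days 8 and 15; pembrolizumab every 3 weeks within 4-week cycles). This is a sensible reading and may be what was meant. The text does not say so.

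**A stronger reading the documents do not support.** A reader might infer that a laboratory value between the two sets of limits is a DLT under one section and not under the other, and so could move the model-based dose allocation. DLT criterion 6 in Section 5.3 is "Failure to meet the required blood parameters for cycle 2 day 1", and its wording matches the title of 5.4. Section 4.3.3 defines neither required parameters nor a DLT. A participant who passes 5.4 does not meet criterion 6, whatever 4.3.3 says. It is true that one DLT more or less can change the recommended level in arms this small, but this conflict does not change the count. In Arm B, moreover, the rules in Section 10.2 restrict the next combination according to the type of DLT, so the model estimate alone would not show what the next participant receives.

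**Conclusion.** The inconsistency is real and bears on safety, but it is limited to who may be re-dosed and who stays on treatment. Section 5.4 admits to a decitabine cycle some participants whom 4.3.3 says should not restart. For creatinine, on the ULN limb, the overlap is 2.0 to 2.4 mg/dL at an assumed ULN of 1.2 mg/dL, a single value at 1.0, and none at 0.9. For bilirubin it is every total of 2 x ULN or more with direct bilirubin within ULN. For ALT it is mainly 2.0 to 3.0 x ULN, or baseline if higher, with liver involvement. Infection is simply absent from 5.4.

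The recovery-grade difference is a conflict only if 7.2 is taken to cover cycle-start doses, which the text leaves open. Removal from treatment is not a third competing instruction; it follows only when a hold exceeds 14 days. How many participants would be affected cannot be estimated from the protocol. Which limit or grade is clinically right is not judged here.

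**What to change.** Reconcile Sections 4.3.3, 5.4, 7.2 and Table 13, as follows:

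- name the section that governs the start of a cycle;
- state whether the creatinine, SGPT, bilirubin and infection conditions of 4.3.3 apply in the decitabine-containing arms (B and C), and if so carry them into that section;
- state which recovery grade applies to cycle-start doses and which to mid-cycle doses, and replace the open exception in 5.4 with a named cross-reference;
- cite 5.4 by number in Section 5.3, criterion 6, so that no site tests it against 4.3.3.

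Which limits and grades apply is for the sponsor to decide. The cost is protocol wording; the laboratory tests are already scheduled. The downside is that, if the tighter limits are kept, some cycles will start later.
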